4.5.3 Treatment Phase

When determining the visit dates, the reference should always be seven days (±3 days). Every attempt should be made to maintain subjects on their original treatment schedule.

4.5.3.1 TV1: Prior to Randomization

The following assessments and activities are performed at this visit:

- Medical history changes from previous visit
- Physical examination changes from previous visit
- Assess concomitant medications, changes from previous visit and prohibited therapies
- Vital Signs

Confidential Page 27 of 73

- Pain assessment (see section 8.9)
- Assess Blood glucose
- Index ulcer Assessments
- Assess signs and symptoms for clinical infection of the index ulcer (see section 8.10.3)
- Index ulcer foot neuropathy Semmes Weinstein 10-point test with vibratory; See section 8.14
- Clean the index ulcer
- Debridement of the index ulcer if applicable (see Appendix E)
- Digital imaging of the index ulcer
- Record Index ulcer measurements
- Assessment of offloading
- Index ulcer closure assessment will be determined by a site Investigator
 - If the index ulcer is 100% re-epithelialized, the subject will be considered a screen failure.
- Assessment of subject's eligibility to continue in the study
- SnapshotNIR (at selected sites)
- If the subject is eligible, randomization will be performed
- If the subject is not eligible, discharge the subject from the study as a screen failure

4.5.3.2 TV1: Randomization

The following assessments and activities are performed at this visit:

- Randomize the subject
- Apply appropriate treatment to index ulcer:
 - Apply SOC therapy with MIRRAGEN™ group 1
 - Apply SOC therapy with FIBRACOL™ group 2
- Apply outer layer dressing
- Ensure offloading of the wound is satisfactory
- Schedule the next study visit for one week later (±3 days)

4.5.3.3 Treatment Phase Visits: Weeks 2-12 (with additional tests week 2, 3, 4, 6 and 7 listed below)

The following assessments and activities are performed at these visits:

- Medical history changes from previous visit
- Physical examination changes from previous visit
- Assess concomitant medications, changes from previous visit and prohibited therapies
- Vital Signs

Confidential Page 28 of 73

- Pain assessment (see section 8.9)
- Assess Blood glucose
- Assessment of offloading
- Index ulcer foot neuropathy Semmes Weinstein 10-point test with vibratory; See section 8.14
- Check for any changes in the subject's health and assess them for any adverse effects and adverse events
- Index ulcer closure assessment will be determined by a site Investigator
 - If the index ulcer is 100% re-epithelialized, the subject will be scheduled for an HCV two weeks later. Please perform all applicable assessments and study procedures.
- Index ulcer Assessments
- Check for signs of clinical infection. If a clinical diagnosis of infection has been made, then
 the subject can be treated with oral antibiotics, but topical antibiotics or antimicrobial
 dressings CANNOT be used on the study ulcer
- Clean the index ulcer
- Debridement of the index ulcer if applicable (see Appendix E)
- Digital imaging of the index ulcer
- Record Index ulcer measurements
- Apply appropriate treatment to index ulcer:
 - Apply SOC therapy with MIRRAGEN™ group 1
 - Apply SOC therapy with FIBRACOL™ group 2
- Ensure offloading of the index ulcer is satisfactory
- Apply outer layer dressing
- The next visit will be scheduled for one week (+/- 3 days)

4.5.3.3.1 TV2: Treatment Visit 2

In addition to the procedures required at every treatment visit, perform the following additional procedures:

SnapshotNIR (at select sites)

4.5.3.3.1 TV3: Treatment Visit 3

In addition to the procedures required at every treatment visit, perform the following additional procedures:

WOUND-Q

4.5.3.3.1 TV4: Treatment Visit 4

In addition to the procedures required at every treatment visit, perform the following additional procedures:

Confidential Page 29 of 73

SnapshotNIR (at select sites)

4.5.3.3.2 TV6: Treatment Visit 6

In addition to the procedures required at every treatment visit, perform the following additional procedures:

- Pregnancy test (blood or urine) if female subject is of childbearing potential
- Assurance of effective birth control if female subject is of childbearing potential

4.5.3.3.3 TV7

In addition to the procedures required at every treatment visit, perform the following additional procedures:

- Evaluate wound for greater than 50% wound area reduction, and if less than 50% healed proceed to End Of Study (EOS1) visit
- SnapshotNIR (at selected sites)
- WOUND-Q

4.5.4 End of Study (EOS1) Visit

The following assessments and activities are performed at this visit:

- Medical history changes from previous visit
- Physical examination changes from previous visit
- Assess concomitant medications, changes from previous visit and prohibited therapies
- Vital Signs
- Pain assessment (see section 8.9)
- Assess Blood glucose
- HbA1c
- Assessment of offloading
 - Index ulcer foot neuropathy Semmes Weinstein 10-point test with vibratory; See section 8.14
- WOUND-Q
- Check for any changes in the subject's health and assess them for any adverse effects and adverse events
- Index ulcer closure assessment will be determined by a site Investigator
 - If the index ulcer is 100% re-epithelialized, the subject will be scheduled for a Healing Confirmation Visit (HCV) two weeks later. Please perform all applicable assessments and study procedures.
- Index Ulcer Assessments
- Check for signs of clinical infection. If a clinical diagnosis of infection has been made, then
 the subject can be treated with oral antibiotics, but topical antibiotics or antimicrobial
 dressings CANNOT be used on the study ulcer

Confidential Page 30 of 73

- Clean the index ulcer
- Debridement of the index ulcer if applicable (see Appendix E)
- Digital imaging of the index ulcer
- Record Index ulcer measurements
- Ensure offloading of the index ulcer is satisfactory and make an appointment for the subject with their desired clinician for follow-up care OR if subject is healed apply outer layer dressing and schedule Healing Confirmation Visit two weeks later (+/- 3 days)
- SnapshotNIR (at select sites)
- Apply outer layer dressing

4.5.5 HCV: Healing Confirmation Visit

Perform the following procedures and assessments at this visit:

- Medial History Changes from previous visit
- Physical examination changes from previous visit
- Assess concomitant medications, changes from previous visit and prohibited therapies
- Vital signs
- Pain assessment (see section 8.9)
- Assess Blood glucose
- Assessment of offloading
- Index ulcer foot neuropathy Semmes Weinstein 10-point test with vibratory; See section 8.14
- Check for any changes in the subject's health and assess them for any adverse effects and adverse events
- If wound has re-opened, clean index ulcer
- If wound has re-opened, apply outer layer dressing
- Debridement of the index ulcer if applicable (see Appendix E)
- Digital imaging of the index ulcer
- If wound has re-opened, index ulcer measurements
- Confirm that the wound remained completely epithelized
- If wound has re-opened, document any other index ulcer assessments. If this is the EOS
 visit, discharge the subject from the study and make an appointment for the subject with
 their desired clinician for follow-up care; otherwise continue subject in study with allocated
 treatment schedule

4.5.6 Unscheduled Visits

Unscheduled visits may be required in addition to the visits detailed above. Additional visits are at the discretion of the Investigator. An example of an unscheduled visit is when a change in dressings is required between scheduled visits. The details of these unscheduled visits with

Confidential Page 31 of 73

subjects will be recorded in the medical records/source documents and on the Unscheduled Visit CRF.

4.5.7 Missed Visits

If a subject misses a visit, the site is to make every effort to have the subject return as soon as possible to make up the visit. Once the subject is seen, he/she is to return to his/her original weekly visit schedule. For example, if a subject was seen regularly on Mondays but missed a scheduled Monday visit and came in on Wednesday, he/she should return the next Monday to maintain his/her weekly Monday visit schedule.

Confidential Page 32 of 73

5 Subject Completion, Success/Failure, Withdrawal and Screen Failure

5.1 Subject Completion

- A subject whose index ulcer has closed will be considered as having completed the study
- A subject who completes the Treatment Phase up to TV7 with the wound healed less than 50% will be considered as having completed the study
- A subject who completes the Treatment Phase but still has an unhealed index ulcer will be considered as having completed the study
- A subject who does not complete the Treatment Phase and still has an unhealed index ulcer will be considered as not completing the study

5.2 Success and Failure

- A subject whose ulcer heals by 13 weeks and has been confirmed as healed two weeks later will be considered a treatment success
- A subject whose ulcer has failed to heal by 50% or greater at TV7 or six weeks after randomization will be considered a treatment failure
- A subject whose ulcer has failed to heal by 13 weeks will be considered a treatment failure
- A subject who is withdrawn from the trial and/or experiences an amputation is also considered a treatment failure

5.3 Premature Withdrawal from the Study

A subject who is randomized into the Treatment Period of the study but who does not complete the study has prematurely discontinued.

All subjects have the right to withdraw at any point during treatment without prejudice. It will be documented whether or not each subject completes the study. If for any subject, study treatment or observations were discontinued, the reason(s) will be recorded.

The Investigator can discontinue a subject at any time if it is considered medically necessary. In addition, the subject will be withdrawn from the study, if any of the following events occur:

- A subject is significantly non-compliant with the requirements of the protocol
- A subject becomes pregnant or does not confirm use of birth control. (Note: the pregnancy will be followed up to term for safety. Relevant safety information collected after the study has been completed will be reported as supplemental information.)
- A subject has revascularization surgery on the lower extremity on which the index ulcer is located
- The subject's index ulcer deteriorates and is infected to the point where there is exposed bone
- An infection episode lasting more than two weeks with no response to allowable treatments

Premature withdrawal from the study may occur if:

 A subject is treated with a prohibited medication. This decision will be made by the Investigator as to whether premature withdrawal is warranted.

Confidential Page 33 of 73

Every attempt should be made to collect follow-up information. The reason for treatment discontinuation or withdrawal from the study will be recorded in the source documents and on the appropriate CRF.

Before a subject is identified as lost-to-follow up, the site should make all reasonable efforts to contact the subject. Three follow-up attempts are required. These attempts must be documented and should include two phone calls and one certified letter.

In the event that a subject is prematurely discontinued from the study at any time due to an adverse effect or adverse event, the procedures in Section 10 of this protocol must be followed.

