3.00Pe	Group 2: SOC primary dressing with FIBRACOL™
Study Design	Multi-center, open label, randomized controlled trial
Sample Size	For this RCT, N = up to 240 subjects
Centers	Up to 15 centers within the United States, Open/competitive enrollment.
Endpoints	Primary endpoint: - The proportion of subjects that obtain complete closure over the 12-week treatment period Secondary endpoints: - The time to achieve complete wound closure of the target ulcer by the end of 12 weeks
	 Percentage wound area reduction from TV1 to TV13 measured weekly with digital photographic planimetry and physical examination
	The number and type of Treatment Emergent Adverse and Serious Adverse Events
	 Change in peripheral neuropathy of the target foot assessed using the standard 10-point Semmes-Weinstein monofilament exam [Time Frame: TV1, TV3, TV7, TV9, and EOS1]
	 Change in pain in the target ulcer assessed using the NPRS scale. [Time Frame: TV1, TV3, TV7, TV9, and EOS1]

Confidential Page 10 of 73

Version 2.0 Date: May 12, 2023 Change in quality of life using WOUND-Q assessment [Time Frame: SV1, TV3, TV7, EOS1] **Exploratory Endpoint:** Difference in cellulitis and/or infection at 12 weeks Use of near-infrared tissue oxygenation imaging assessment of wounds at select sites to evaluate changes in vascularization/oxygenation of wounds with treatment (Kent Imaging SnapshotNIR: Time Frame: SV1, TV1 pre-randomization, TV2, TV4, TV7, and EOS1. Safety There is no formal safety objective for this study as MIRRAGEN™ and FIBRACOL™ are commercially available, 510K FDA cleared dressings for diabetic foot wounds. Therefore, in accordance with FDA regulations, adverse reactions to the dressings will be recorded and provided to the study Sponsor for required FDA reporting and will be concurrently reported to all Investigators and IRBs. Adverse events associated with application of standard of care dressing will be collected during the course of the study. Collection and reporting of any adverse reaction data, in accordance with FDA regulations and adverse events associated with dressing application will ensure study subject safety.

Surveillance Schedule

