7.2 Concomitant Medications

The subject may be administered any necessary medications, at the discretion of the Investigator; provided such medications are not applied topically to the index ulcer surface (topical medication can be applied to other surfaces around the ulcer or other non-reference ulcers).

All medications and therapies administered or taken by the subject beginning 30 days prior to signing the ICF and throughout the study will be recorded in the source documents and for randomized subjects, on the appropriate CRF.

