7.3 Prohibited Medications and Therapies

The following treatments and medications are prohibited 30-days prior to screening period and throughout the trial:

- Any cellular and/or tissue-based products or wound dressings that include growth factors (e.g., EpiFix, Regranex, Dermagraft, Apligraf, GraftJacket, OASIS, Primatrix, Matristem)
- Revascularization surgery on the lower extremity with the index ulcer

Confidential Page 39 of 73

Radiation therapy to the foot

Excluded at SVI

- Topical antibiotics* or other topical agents, including or containing silver, honey, hydrofera blue, etc. (with the exception of anesthetics used during debridement)
- Systemic steroids/oral corticosteroids in excess of 10mg daily dose. (Note: inhaled steroids are acceptable)
- Other immunosuppressive agents and chemotherapy
- Cytotoxic therapies
- Negative pressure wound therapies
- Hyperbaric oxygen
- Any other investigational treatment/medications in the Investigator's opinion are likely to seriously impact wound healing
- Heat lamps
- UV lights
- Whirlpool baths
- Water PiksTM
- Jet water streams (other than gentle water irrigation)
- Wound cleansers that contain active ingredients and are not just normal saline (e.g., Hypochlorous Acid, Vashe, ExSept, Preplt, etc.)
- Selective COX-2 inhibitors (such as Celecoxib)

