12.3 Reporting Protocol Deviations

The Investigator is obligated to follow the protocol without departure from the requirements written in the protocol. Any time there is deviation from any protocol requirements, a protocol deviation is required to be reported. If the deviation may impact subject participation, the Sponsor should be notified and will make the determination as to whether the subject will continue in the study. The Sponsor also has the right to discontinue the subject for protocol violations. The IRB may also have to be contacted if safety to the subject or if the scientific soundness of the study is involved. All protocol deviations must be documented in the CRFs. Protocol deviations will be tracked at the site level and (by the Sponsor) at the study level for the duration of the trial.

Confidential Page 55 of 73

13 Ethics and Regulatory Requirements

This study is to be conducted in accordance with the requirements of this protocol and in accordance with principles consistent GCP, ICH E6, HIPAA regulations (45 CFR Part 164) and the Belmont Principles of respect for persons, beneficence, and justice. No protocol changes will be implemented without prior review and approval of the IRB, except where it may be necessary to eliminate an immediate hazard to a study subject. In such a case, the change will be reported to the IRB as soon as possible, according to IRB requirements. Additionally, all products used in this study are manufactured, handled, and stored in accordance with their FDA labeling.

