Appendix E: Debridement

Many chronic wounds contain necrotic tissue that has a black or dark gray appearance. Wound eschar is usually full-thickness, dry devitalized tissue arising from prolonged ischemia and slough is an adherent fibrous material commonly creamy yellow in appearance. Chronic wounds can also have colonized bacteria in the form of biofilm or cells, particularly along the margins of a wound, which have stopped dividing - a process known as senescence. Finally, devitalized tissue and biofilms can harbor high levels of cytokines or cellular remnants that maintain the wound in the inflammatory or proliferative stages of healing, through cellular trafficking processes. Any of these factors can disrupt the normal stages of wound healing.

Debridement is the process by which these elements are removed to permit healing, in effect changing the stalled chronic wound into an acute wound. In this clinical study, we have restricted the type of debridement to sharp debridement.

Technique

Sharp debridement comprises the following elements:

- 1. The index ulcer and the surrounding skin are prepped with water or Saline.
- 2. Anesthesia, topical or injected, is applied to the ulcer as necessary to reduce subject discomfort.
- 3. Using a sterile technique, all non-viable tissue in the wound bed is excised using a scalpel and scissors.
- 4. Excessive bleeding is controlled by using direct pressure, but cautery may be employed if necessary.

If extensive surgical debridement is necessary during the run-in period (e.g., general anesthesia is required), the patient is not a candidate for this trial. Likewise, if other forms of debridement (e.g., enzymatic) are required during run-in, based on the opinion of the treating clinician, the subject should be screen failed. During the Treatment Phase of the trial, other forms of debridement are NOT permitted. If this should happen, the type of debridement should be noted in the CRF, using other forms of debridement besides sharp debridement more than once during the treatment phase will result in the subject being withdrawn from the trial.

Although there is increasing evidence that more frequent debridement results in faster healing on average, the frequency and level of debridement in this trial is left up to the treating physician's judgment. Excessive debridement can be as deleterious to healing as too little debridement.

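### After off-protocol treatment, withdrawal is left to an unmasked Investigator and overlaps with a Sponsor decision, so the same exposure can be scored as failure or success

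*Combined protocol and SAP*

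**What the plan says.** The synopsis describes the design as "Multi-center, open label, randomized controlled trial".

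**Withdrawal.** Section 5.3 has a list of events that require withdrawal and a separate entry for events that may lead to it. The second contains: "A subject is treated with a prohibited medication. This decision will be made by the Investigator as to whether premature withdrawal is warranted." No criteria follow. Section 12.3 has the Sponsor decide whether a subject continues when a deviation may affect participation, and adds: "The Sponsor also has the right to discontinue the subject for protocol violations."

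**Scoring.** Section 5.2 states: "A subject who is withdrawn from the trial and/or experiences an amputation is also considered a treatment failure". The same section counts an ulcer healed by 13 weeks and confirmed two weeks later as a success, with no condition about prohibited treatment. Section 9.2 says that withdrawn subjects enter the ITT analysis of the primary endpoint through imputation, by methods left to a SAP to be written before database lock.

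**What is prohibited.** Section 7.3 opens with a list described as "prohibited 30-days prior to screening period and throughout the trial". Partway down, a sub-heading reads "Excluded at SVI". Beneath it stand, among others, topical agents, systemic steroids above a stated dose, negative pressure therapy, hyperbaric oxygen and COX-2 inhibitors. Section 7.2 says: "The subject may be administered any necessary medications, at the discretion of the Investigator", provided that they are not applied topically to the index ulcer.

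**The concern.** Withdrawal is normally an administrative matter, and the endpoint is assessed separately. Here Section 5.2 ties them together, so whoever decides on withdrawal also influences the primary outcome. If that person knows the arm and has no written criteria, the handling can differ between arms without anyone breaking the protocol. A control subject given a listed therapy might be withdrawn and counted as a failure, while a comparable MIRRAGEN subject is kept in, closes, and counts as a success, or the reverse. Closures helped by another active therapy could also be credited to the allocated dressing. The risk is bias and a false positive result. Loss of power is not the problem.

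The adjudication panel in Section 4.3.2 judges healing from photographs. It has no role in withdrawal, so it does not protect against this.

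**Working it through.** **1. The rules side by side, for a subject who receives a listed treatment after randomisation**

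| Question | Section | Answer |
|---|---|---|
| Who decides on withdrawal? | 5.3 | Investigator |
| | 12.3 | Sponsor, if the deviation may affect participation |
| By what criteria? | 5.3, 12.3 | None stated |
| Outcome if withdrawn | 5.2 | Failure |
| | 9.2 | Imputed in ITT, method not given |
| Outcome if kept, closed and confirmed | 5.2 | Success |

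Section 5.3 also makes withdrawal compulsory for significant non-compliance, which it does not define. One exposure could be read as falling under that entry or under the optional one. The optional entry speaks only of a medication, whereas Section 7.3 covers medications and therapies, so negative pressure and hyperbaric oxygen have no express consequence there.

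**2. The plan's own figure**

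Inputs from Section 9.2: n = 120 per arm, closure 0.70 versus 0.35, two-sided alpha 0.049 (z = 1.9686), pooled Z-test.

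- Pooled SE under H0: √(0.525 × 0.475 × 2/120) = 0.06447. Critical difference: 1.9686 × 0.06447 = 0.1269.
- SE under HA: √((0.70 × 0.30 + 0.35 × 0.65)/120) = 0.06038.
- Power: Φ((0.35 − 0.1269)/0.06038) = Φ(3.695) = 0.9999, which reproduces the stated 100%. This is the fixed-sample formula, because the sequential boundary is not specified.

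**3. Illustration of arm-dependent handling**

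Assumptions, none of them in the documents: no true difference; true closure rate p in both arms; a share u of each arm is exposed and closes at rate p; a share w of the exposed is withdrawn and scored as failure, with w different in the two arms. The observed closure rate in an arm is then p(1 − u·w).

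Example with p = 0.35, u = 10%, w = 0 in the MIRRAGEN arm and 1 in the FIBRACOL arm:
- Observed rates 0.35 and 0.35 × 0.90 = 0.315; difference 0.035.
- Pooled SE 0.06082; critical difference 0.1197; unpooled SE 0.06078.
- Probability of rejection: Φ((0.035 − 0.1197)/0.06078) + Φ((−0.035 − 0.1197)/0.06078) = Φ(−1.394) + Φ(−2.546) = 0.0816 + 0.0055 = 0.087.

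Two-sided type I error (nominal 0.049):

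| Exposed share u | Withdrawn, MIRRAGEN / FIBRACOL | p = 0.35 | p = 0.70 |
|---|---|---|---|
| 5% | 0% / 100% | 0.058 | 0.088 |
| 5% | 25% / 75% | 0.051 | 0.059 |
| 10% | 0% / 100% | 0.087 | 0.206 |
| 10% | 25% / 75% | 0.058 | 0.087 |
| 20% | 0% / 100% | 0.212 | 0.610 |
| 20% | 25% / 75% | 0.088 | 0.199 |

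Equal handling in both arms leaves the error at 0.049. Each decision on an ulcer that would close moves one arm by 1/120 = 0.83 percentage points.

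**4. Power under the planned effect**

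If 20% are exposed, all of them are withdrawn in the MIRRAGEN arm and none in the FIBRACOL arm, the observed rates are 0.56 and 0.35 and power is still 0.91.

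**The case against.** **The prohibited list probably does apply after SV1.** A reader might infer from the sub-heading in Section 7.3 that negative pressure, hyperbaric oxygen or silver dressings are allowed after randomisation. The documents do not support that. Prohibited therapies are checked at every visit in Table 1. Section 7.1.1 bars antiseptic cleansers for the whole study, and Sections 4.5.3.3 and 8.10.3 bar topical antibiotics and antimicrobial dressings during treatment. Section 7.5 lists the approved dressings, and Section 7.4 allows only therapies not otherwise prohibited. Section 7.2 excludes topical use on the index ulcer. What stands is an unclear label. For negative pressure and hyperbaric oxygen no other section settles the point, and Section 7.2 is not aligned with the systemic agents in Section 7.3.

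**Different events may have different consequences.** Compulsory withdrawal after revascularisation (Section 5.3), or after non-sharp debridement used "more than once during the treatment phase will result in the subject being withdrawn from the trial" (Appendix E), is not in itself a contradiction of the optional rule for a medication. This stands. The clear overlap is between Sections 5.3 and 12.3 on who decides.

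**Section 9.2 imputes withdrawn subjects.** A reader might infer that withdrawal by itself fixes the ITT outcome. That is not settled, because Section 9.2 imputes these subjects and plans sensitivity analyses. It does not remove the problem either: Section 5.2 says failure, Section 9.2 says imputation, and neither refers to the other.

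**What is known about masking.** No section says that the photograph adjudicators are masked to arm; blinding is mentioned only for the eligibility panel before randomisation. That the Sponsor knows the arm is inferred from the open-label design and the absence of any statement that it is masked.

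**The size is assumed.** True. The 0%/100% split is an extreme, and at 5% exposure with 35% closure it moves the error only to 0.058.

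**Conclusion.** The point holds in limited form. As written, the plan lets an Investigator who knows the arm, and a Sponsor who probably does, decide without criteria on withdrawals that Section 5.2 turns into failures, while a retained subject with the same exposure can count as a success. Section 9.2 leaves the analysis of those withdrawals unresolved. The scope of Section 7.3 after randomisation is unclear for some items, although most of the text points to the whole list applying throughout.

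The documents do not show that such exposures will be common or that anyone will handle the arms differently, so no actual bias can be estimated. At an assumed 10% exposure, type I error would be about 0.06 to 0.09 for a 35% closure rate and 0.09 to 0.21 for 70%, depending on how uneven the handling is. These figures assume that withdrawal is scored as failure and that exposed ulcers close at the same rate as the others. The weakness should be corrected, and it is cheap to correct. It does not undermine the planned power.

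**What to change.** - **Reconcile the text.** Sections 5.3, 7.2, 7.3, 12.3 and Appendix E must agree on which items apply after randomisation and on who decides about withdrawal. Which clinical rule is right is for the sponsor and its clinicians, and treatment of the individual patient stays with the treating clinician.
- **Separate scoring from withdrawal.** Pre-specify one rule, the same in both arms, for any subject who receives a therapy on the reconciled throughout-trial list, local or systemic, before confirmed closure. In line with Section 5.2, score that subject as not closed in the primary analysis, whether or not the subject is withdrawn. Restricting the rule to therapies applied to the index ulcer would miss hyperbaric oxygen, revascularisation and systemic agents.
- **Add a sensitivity analysis** that uses observed closure where follow-up exists. Analysing closure as observed is a legitimate alternative, and this shows whether the choice matters.
- **Apply the rule without allocation.** Use the concomitant-treatment CRF with the arm removed. Section 7.2 already requires these therapies to be recorded.
- **Align Section 9.2 with Section 5.2**, so that it is clear when a withdrawn subject is a failure and when the outcome is imputed.

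The cost is protocol and SAP wording, plus a short masked review of data already collected. The downside is that a few closures after off-protocol therapy will count as failures in both arms.
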